Percentages of subjects with immune response will be calculated along the corresponding twosided exact (Clopper-Pearson) binomial CIs. GMTs will be summarized by treatment group and visit day along with the corresponding two-sided 95% CIs, by exponentiating the corresponding log-transformed means and their 95% CIs. Two-sided 95% CIs for the difference in proportions of participants demonstrating SCR and SPR between a Tri-NIV group and the Fluzone HD group will be based on the Newcombe hybrid score (METHOD = SCORE riskdiff-option for PROC FREQ in SAS). The within-group geometric mean ratio (GMRpost/pre) will be conducted using paired t-test based on log-transformed values. Then, the mean difference and the corresponding 95% CI limits will be exponentiated to obtain the GMT ratio and the corresponding CI.

Reverse cumulative distribution displays of HAI and MN titers for each virus strain will be produced in which Day 0 and Day 21 distributions will be displayed separately by treatment group. Titers reported below the lowest limit of quantitation [LLOQ] (ie, below the starting dilution of assay reported as "< 10") will be set to half that limit (ie, 10/2 = 5).

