7 ANALYSES ADDRESSING PROTOCOL OBJECTIVES

7.1 Analyses of Primary Objectives of immunogenicity

The analysis of primary immunogenicity endpoints will be conducted by using PP and ITT population, with PP population as the primary analysis. No missing data will be imputed.

Antibody titers specific for the HA receptor binding domains of each of the virus strains included in Tri-NIV, H1N1, H3N2, and Bv, will be analyzed.

- Geometric mean titers (GMT) of Antibody titers specific for the HA receptor binding domains of each of the virus strains and their 95% CIs will be summarized by treatment at baseline (pre-vaccination on Day 0) and post vaccination on Day 21. GMT will be calculated as the antilog of the mean of the log-transformed HAI titers for a given treatment group. Lognormal distribution is assumed for antibody titer to construct confidence interval.
- Between-group geometric mean ratio (GMR_{new/ref}) and its 95% CI for each of the Tri-NIV groups against active comparator group Fluzone HD will be conducted using two-sample t distribution. A sample SAS code is given below:

```
proc ttest data=fludata alpha=0.05;
by Visit;
class grp;
var log(HAI D21);run;
```

• Within-group geometric mean ratio (GMR_{post/pre}) for each arm will be conducted using paired t distribution. A sample SAS code is given below:

```
proc ttest data= fludata_Long alpha=0.05;
by Visit Group;
PAIRED log(HAI D21)*log(HAI D0);run;
```

Seroconversion rate (SCR) is defined as the percentage of subjects with either a baseline HAI titer < 1:10 and a post-vaccination titer ≥ 1:40, or a baseline HAI titer ≥ 1:10 and a 4-fold increase in post-vaccination HAI titer relative to baseline. The 95% confidence interval will be constructed by Clopper-Pearson method with the following sample SAS code:

```
proc freq data=fludata ;
by treatment;
tables seroconvind/ nocum norow binomial;
exact binomial;
run;
```

• Seroconversion rate difference is defined as the difference of seroconversion rates between each of the Tri-NIV vaccine groups and Fluzone HD group. The Chi-Square p-value for testing the equality of SCRs between two groups will be derived with continuity adjustment. The Newcombe method will be used to construct its 95% confidence interval with the following sample SAS code:

```
proc freq data = fludata;
tables trtan*seroconvind / riskdiff (column=2 cl=(newcombe)) chisq;
run ;
```

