- Seroprotection rate (SPR) is defined as the percentage of subjects with an HAI titer ≥ 1:40 by treatment group. The 95% confidence interval will be constructed similarly by Clopper-Pearson method.
- Seroprotection rate difference is defined as the difference of SPRs between each of the Tri-NIV groups and Fluzone HD group. The 95% CI will be constructed similarly to that for SCR difference.

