9 SAMPLE SIZE CONSIDERATIONS

The sample size is chosen as adequate for an initial description of safety and immunogenicity to direct future development and dosing. No hypothesis tests are specified and the sample size is not intended to support any statistical contrast of Tri-NIV with Fluzone HD. For safety endpoints, the probability of observing at least one adverse event among 110 subjects for each of the two Tri-NIV groups or 220 for the two Tri-NIV groups combined, are > 90% if the true rate of such events is 2.1% and 1.1%, respectively. With 110 for each of the two Tri-NIV group or 220 for the two Tri-NIV groups combined, observing no adverse events of interest (eg, vaccine-related SAE) would represent an upper bound of the one-sided 95% CI on the percentage of such events of 2.7% and 1.4%, respectively.

Tri-NIV is expected to be comparable (statistically non-inferior) to the currently licensed Fluzone HD in terms of SCR. If the underlying SRRs is 70% for both the Tri-NIV and active control groups for a given strain, with 100 subjects in each group, the trial has a 46% power to detect -0.10 non-inferiority (NI) margin. If the underlying SRR is 50%, the power will be 41%.

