10 PRELIMINARY UNBLINDED AND FINAL ANALYSES

An unblinded analysis will be conducted upon completion of all Day 21 visits, which will include all available immunogenicity data through Day 21 at the time of the analysis and safety data (inclusive of clinical laboratory safety assessments) through Day 21. An unblinded review will be conducted of all available immunogenicity and safety data (including clinical assessments and concomitant medications) upon completion of all Day 21 visits. For the review, treatment codes will only be unblinded after all subjects have completed the Day 21 visit, the data are monitored, all applicable queries are resolved, and the database locked. The data and analyses provided in the review will be considered final for the material contained therein, and will not change.

In order to execute this review, a select group of study staff will be unblinded at the CRO and at Novavax. No individual unblinded at a subject treatment level will be involved in follow-up safety monitoring or immunogenicity determination. Specifically, personnel at the clinical

study site including, investigators and study staff, research site, immunology laboratory, and study subjects will remain blinded to treatment assignments until the end of study (ie, Day 385).

Since study procedures and monitoring practices will not change following the review and the study will not be terminated prematurely on the basis of these data, no decision cut points or stopping rules will be stipulated. No hypothesis testing will be performed.

Immunogenicity and safety analyses from the unblinded review may be presented in an abbreviated Unblinded CSR drafted by the Sponsor that will be submitted to regulatory authorities as needed. The final CSR will present the balance of all disposition, immunogenicity and safety data (inclusive of concomitant medications) through Day 364 (the scheduled end of study. The database will be locked and the final study report prepared, when all of the above data have been entered, reviewed, and all queries related to the data have been addressed.

The final CSR will present the balance of all immunogenicity and safety data through Day 364 (the scheduled end of study). The database will be locked and the final study report prepared, when all of the above data have been entered, reviewed and all queries related to the data have been addressed.

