12 DATA HANDLING CONVENTIONS

All statistical analyses will be 2-tailed and assessed at the 5% significance level.

All output will be incorporated into Microsoft Word or Excel files, or Adobe Acrobat PDF files, sorted and labeled according to the International Conference on Harmonisation (ICH) recommendations, and formatted to the appropriate page size(s).

Tabulations will be produced for appropriate demographic, baseline, and safety parameters. For categorical variables, summary tabulations of the number and percentage of subjects within each category (with a category for missing data) of the parameter will be presented. For continuous variables, the number of subjects, mean, median, standard deviation (SD), minimum, and maximum values will be presented.

For all analyses, a p-value of < 0.05 will be considered statistically significant. All references to analysis of GMT will be interpreted as analysis of the log₁₀ of titer values or of the reciprocal titers (eg, the reciprocal titer of 1:160 is the number 160) or of concentrations.

The individual immunogenicity titer values recorded as below the LLoQ of the assay will be set to half LLoQ for the purposes of GMT, GMR analyses. The LLoQ values will be provided by corresponding lab or CRO as part of the data transfer.

All descriptive statistical analyses will be performed using SAS statistical software Version 9.3 or higher in a Windows environment, unless otherwise noted. Medical history and AEs will be coded using the MedDRA Version 20.0.

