12.3 Multiple Comparisons/Multiplicity

No multiplicity adjustment will be applied.

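### SAP 7.1 orders significance tests on seroconversion rates, and SAP 12 calls p < 0.05 significant, in a trial that SAP 9 and 10 say has no hypothesis testing

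*SAP*

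**What the plan says.** Statements that the trial is descriptive:

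- SAP 9: "No hypothesis tests are specified and the sample size is not intended to support any statistical contrast of Tri-NIV with Fluzone HD". Protocol 10.5 says the same.
- SAP 10, in the text on the Day 21 unblinded review: "No hypothesis testing will be performed".
- Protocol 10.4.1.2 plans "Two-sided 95% CIs for the difference in proportions of participants demonstrating SCR and SPR between a Tri-NIV group and the Fluzone HD group", by the Newcombe method. It plans no p-value for these differences.

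Statements that bring in a test:

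- SAP 7.1, for the SCR difference of each Tri-NIV group from Fluzone HD: "The Chi-Square p-value for testing the equality of SCRs between two groups will be derived with continuity adjustment". The sample code carries the CHISQ option.
- SAP 12: "All statistical analyses will be 2-tailed and assessed at the 5% significance level", and later "For all analyses, a p-value of < 0.05 will be considered statistically significant".
- SAP 12.3: "No multiplicity adjustment will be applied".

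For the seroprotection rate (SPR) difference, SAP 7.1 asks for an interval only: "The 95% CI will be constructed similarly to that for SCR difference". SAP 13 declares no change from the protocol's analyses (NA).

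**The concern.** A programmer who follows SAP 7.1 and 12 will print a p-value for each SCR difference, and the report will call some of them statistically significant. That contradicts SAP 9 and 10 and adds an analysis that the protocol does not plan and SAP 13 does not declare. Comparing Tri-NIV with Fluzone HD is planned and is not in question. The conflict lies in the test and the significance verdict.

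Two things follow. First, a trial not sized for these contrasts would carry significance labels on a primary immunogenicity endpoint, from several unadjusted tests. Its stated purpose is to guide later development and dosing, and the Day 21 results may go to regulators in an abbreviated report. Second, the continuity-adjusted p-value and the Newcombe interval are calibrated differently, so the same line of a table can give two answers.

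**Working it through.** **Inputs from the documents.** Two-sided 5% level (SAP 12). Two Tri-NIV groups, each against one shared Fluzone HD group, for three strains (SAP 7.1): 2 × 3 = 6 primary SCR tests. About 110 subjects per group (SAP 1.1); SAP 9 also uses 100. Allocation 1:1:1 (SAP 1.2). SAP 9 mentions underlying rates of 50% and 70%.

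**Assumptions.** No true difference, n = 100 to 110 per arm, SCR 30% to 70%, and strains independent unless stated.

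The plan gives no false-positive figure to reproduce.

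**Step 1: the test.** With x1 and x2 responders among n per arm, N = 2n and s = x1 + x2, the continuity-adjusted statistic is

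X² = N(|x1(n − x2) − x2(n − x1)| − N/2)² / [s(N − s)n²], with p < 0.05 when X² > 3.841.

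**Step 2: chance of at least one label.** All binomial outcomes were enumerated exactly. Because the comparator is shared, the error for one strain is e = 1 − E[(1 − P(reject | comparator result))²]. Over three independent strains it is 1 − (1 − e)³.

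| n per arm | SCR | size of one test | per strain, e | at least one of six |
|---|---|---|---|---|
| 100 | 0.3 or 0.7 | 0.035 | 0.064 | 0.180 |
| 100 | 0.5 | 0.040 | 0.073 | 0.204 |
| 105 | 0.3 or 0.7 | 0.035 | 0.064 | 0.181 |
| 105 | 0.5 | 0.032 | 0.060 | 0.169 |
| 110 | 0.3 or 0.7 | 0.035 | 0.065 | 0.182 |
| 110 | 0.5 | 0.036 | 0.067 | 0.187 |

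For example, n = 100 and SCR 0.5: 1 − (1 − 0.0733)³ = 0.204.

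**Step 3: correlated strains.** The three titers come from the same subjects, so independence is an upper case. By simulation (60,000 runs per setting), the chance is 16.0–19.6% at latent correlation 0.5 and 14.1–17.4% at 0.8.

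**Step 4: p-value against interval.** Take 70/110 against 55/110, a difference of 13.6 points. The cross-product difference is |70 × 55 − 55 × 40| = 1650, and the denominator is 125 × 95 × 110² = 143,687,500.

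- Adjusted: 220 × (1650 − 110)² / 143,687,500 = 3.63, p = 0.057.
- Uncorrected: 220 × 1650² / 143,687,500 = 4.17, p = 0.041.
- Newcombe interval, from Wilson limits 0.543–0.720 and 0.408–0.592: lower 0.1364 − √[(0.636 − 0.543)² + (0.592 − 0.500)²] = 0.006; upper 0.1364 + √[(0.720 − 0.636)² + (0.500 − 0.408)²] = 0.261.

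The interval, 0.6 to 26.1 points, excludes zero, yet under SAP 12 the p-value is not significant.

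By enumeration, the interval excludes zero with adjusted p ≥ 0.05 in 1.3–1.6% of comparisons under no difference, and in 5.4–6.1% at true rates of 0.50 v 0.63, 0.50 v 0.65 and 0.30 v 0.44. The reverse did not occur in any setting.

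**Step 5: what intervals alone would do.** Under the same null and independent strains, at least one of six unadjusted Newcombe intervals excludes zero in 22.8–27.4% of trials. The uncorrected chi-square gives practically the same range.

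**The case against.** **The error rate is not the harm, and the fix does not lower it.** Nothing is decided on these p-values, and interval-only reporting excludes zero somewhere more often (23–27%) than the adjusted test rejects (17–20%). This is correct. The defect is a test and a verdict in a plan declared descriptive; the percentage only shows how often an unsupported label would appear.

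**The no-testing sentences are narrower than they look.** The SAP 10 sentence closes a paragraph about decision rules at the Day 21 review, SAP 9 is a sample-size section, and protocol 10.4.1.2 itself names a paired t-test for a descriptive ratio. This softens the conflict without removing it. The SCR data are Day 21 data and fall within that review, the SAP 9 statement is general, and SAP 7.1 and 12 speak openly of testing and significance.

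**The figures depend on assumptions.** They need all six nulls to be true and mid-range rates. At SCR 90% the chance falls to 13–14%. The 5–6% discordance is near its peak: it is 2.4–2.7% at 0.50 v 0.55 and 1.1–1.5% at 0.50 v 0.75. On the other side, six is a minimum count, since SAP 7.1 also covers the ITT population and SAP 7.2 and 7.3 reuse the methods for further strains.

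**A continuity adjustment is a legitimate conservative choice.** Agreed. It matters only because it sits beside an interval calibrated differently.

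**SAP 9 would still contain non-inferiority power text.** True: its second paragraph gives 46% and 41% power for a −0.10 margin, which protocol version 4.0 removed from the protocol. That is a separate defect, and the change proposed here does not cure it.

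**Conclusion.** The concern holds. SAP 7.1 and 12 order tests and significance labels that SAP 9, SAP 10 and protocol 10.5 rule out and that protocol 10.4.1.2 does not plan. With no true difference, 100–110 per arm, SCR 30–70% and a shared comparator, at least one of the six primary SCR tests would be labelled significant in 16.9–20.4% of trials with independent strains, or about 14–17% at latent correlation 0.8. Some p-values would also disagree with the interval beside them, always with the interval excluding zero and p not below 0.05. The consequence is over-reading of nominal results in a descriptive phase 1/2 trial. It should be corrected, but it does not threaten a confirmatory conclusion, because none is planned.

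**What to change.** - In SAP 7.1, delete the chi-square sentence and the CHISQ option in the sample code.
- In SAP 12, delete the sentence setting a 5% significance level and the sentence calling p < 0.05 statistically significant.
- Report SCR differences as SPR differences are reported: two-sided 95% Newcombe intervals, described as descriptive and not adjusted for multiplicity.

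If the sponsor prefers to keep p-values, label them nominal and attach no significance verdict. Using the uncorrected chi-square would make them agree closely with the intervals (disagreement in at most 0.6% of comparisons in the settings studied); that choice is optional.

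The cost is SAP wording. The sponsor loses only nominal p-values that the protocol does not plan. The change removes the contradiction over these tests and the unsupported labels. It does not control error across the six comparisons, and the report should say so.

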7.2 Analyses of Secondary Objectives of Immunogenicity

Antibody titers specific for the HA receptor binding domains of at least 2 historic A virus strains (one H1N1 and one H3N2) as measured by the HAI assay will be summarized as follows using the same statistical approaches as the primary immunogenicity endpoints:

- Geometric mean titer (GMT) defined as the antilog of the mean of the log-transformed HAI titers for a given treatment group.
- Geometric mean ratio (GMR) defined as the ratio of post-vaccination and pre-vaccination HAI GMTs within the same treatment group (designated as GMRPost/Pre).
- Seroconversion rate (SCR) defined as the percentage of subjects with either a baseline HAI titer < 1:10 and a post-vaccination titer \geq 1:40, or a baseline HAI titer \geq 1:10 and a 4-fold increase in post-vaccination HAI titer relative to baseline.
- Seroprotection rate (SPR) defined as the percentage of subjects with an HAI titer \geq 1:40.

7.3 Analyses of Exploratory Objectives of Immunogenicity

The following exploratory antibody titers will be summarized using the same statistical approaches as the primary immunogenicity endpoints.

- HAI and neutralizing antibody titers specific for a contemporary B/Yamagata virus strain.
- Levels of antibodies competitive with broadly-neutralizing monoclonal antibodies to HA of varying specificities, as measured by competitive-binding in a biosensor assay.

8 SAFETY ANALYSES

All safety analyses will be based on the safety population. Adverse events are defined as any unfavorable or unintended change in the physical, psychological, or biochemical condition of the subject. An AE temporally related to participation in the study will be documented whether or not considered related to the test article. This definition includes intercurrent illnesses and injuries, and exacerbations of pre-existing conditions. Stable pre-existing conditions which do not change in nature or severity during the study are not considered AEs; however, these should be collected as part of the medical history. AEs will be considered treatment emergent from the date and time of the first administration of the investigational product.

8.1 Analyses of Primary Objectives of Safety

Safety will be assessed in the Safety population including all subjects who receive any test article, and will be summarized overall and by treatment group based on solicited local and systemic adverse events, 21-day all AE profile (including adverse changes in clinical laboratory parameters) by Medical Dictionary for Regulatory Activities (MedDRA) preferred term, severe, related (possibly, probably, or definitely), and one-year MAEs, SAEs and SNMCs profiles. The number and percentage (95% CI) of subjects in each treatment group with a given term will be summarized. A listing and narratives of SAEs will also be produced.

Solicited adverse events occurring in the first 7 days after each dose of test article will be presumed to be related; and severity will be graded by specific definitions included in the protocol and subject diary. Unsolicited adverse event summaries by relationship to test article will be categorized as "not related" (including "unrelated" or "unlikely") or "related" (including "possible", "probable", and "definite"). For multiple occurrences of an adverse event in the same subject, a subject will be counted only once, using the most severe or most related occurrence for the summarization by severity or relationship to test article, respectively.

Solicited adverse events will not be coded, and will be summarized by solicited term only. All unsolicited adverse events will be coded using MedDRA version 20.0.

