# 1.10 Risks Associated with Fluzone HD

Fluzone HD has been the subject of several large clinical trials including over 18,500 recipients of Fluzone HD contrasted to over 17,200 subjects concurrently treated with Fluzone, a standard-dose (15µg of each HA) trivalent inactivated influenza vaccine. In these studies, local injection site solicited adverse events typical of intramuscular vaccine reactogenicity and occurring in the first 7 days after dosing occurred between 1.3- and 1.6-fold more commonly in the Fluzone HD recipients than Fluzone recipients, including a 35.6% incidence of local injection site pain, 14.9% erythema, and 8.9% swelling. Systemic complaints such as myalgia, malaise, and headache were only modestly more common in high-dose Fluzone recipients, occurring in approximately 17 to 21%. Fever occurred in 3.6% of Fluzone HD vaccinees. The majority of all these events were mild in severity. Considering the longer term adverse event profile, Fluzone HD was not distinguishable from standard dose influenza vaccine.

A variety of events have been reported in the post-marketing experience with Fluzone and Fluzone HD, but a causal relationship has not been established. Information regarding the post-marketing safety data for Fluzone products is available in the Package Insert, which will be supplied to Investigators. Of note, Fluzone HD is produced in eggs, in common with the majority of inactivated vaccines. Therefore, subjects with known history of severe allergic reaction to any influenza vaccine, or allergy to egg proteins, should not receive Fluzone HD. Additionally, subjects with a history of Guillain-Barré syndrome within 6 weeks of any influenza vaccine should not receive Fluzone HD or be enrolled in this trial (see trial exclusion criteria in Section 5.2).

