# **10.4 Analyses Addressing Protocol Objectives**

#### 10.4.1 Analyses of Primary Objectives

#### 10.4.1.1 Safety

Safety analysis will be descriptive and based on the safety population, defined as all subjects who received a dose of trial treatment. Safety will be summarized overall and by individual treatment arms based on solicited short-term reactogenicity post-injection on Day 0, 21-day all AE profile by MedDRA preferred term, and 1-year MAE, SAE, and SNMC profiles post-injection on Day 0. Note: The 21 day post vaccination all adverse event profile will include all unsolicited AEs reported from test article receipt until the day preceding the rescue dose, ie, events with onset dates between days 0 to 20 for subjects who receive the rescue dose as scheduled on day 21. Rules for defining the dataset in subjects who receive the rescue dose before or after day 21, or no rescue dose, are detailed in the statistical analysis plan. All AEs, MAEs, SAEs, and SNMCs will be tabulated by severity, related (possibly, probably, or definitely vs. non-related per investigator assessment), and severe and related. The number and percentage (with 95% CI) of subjects in each treatment group with a given term will be summarized. Clinical laboratory data will be summarized by means and 95% confidence interval, minima and maxima, at Day 0 and Day 21 in each treatment group, as well as means and 95% confidence interval of change from baseline at Day 21. Changes from baseline will also be summarized at Day 21 for each treatment group in terms of the proportion of subjects with no change in toxicity grade versus proportions with one, two, or three grade changes. A listing and narratives of SAEs will also be produced.

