Several features of Tri-NIV warrant clinical investigation of its safety and immunogenicity among older adults. In ferrets, Tri-NIV administered with Matrix-M1 adjuvant elicited rapid and robust immune responses in terms of geometric mean HAI titers with responses exceeding those induced by Fluzone HD. Secondly, geometric mean 50% microneutralizing (MN) titers against a broad panel of historic H3N2 strains tested, dating to 1999 and spanning a number of clinically-significant antigenic drift events, showed 2 to 214-fold higher titers among animals given Tri-NIV with Matrix-M1 adjuvant than among animals given Fluzone HD. These data suggest that Tri-NIV may elicit antibodies to broadly-neutralizing epitopes capable of providing greater drift strain protection, even against strains such as A/HongKong/4801/2014, which are associated with impaired influenza vaccine efficacy in humans. While cross-lineage B virus antibody responses were not seen in naïve animals, the possibility of such responses should be considered, and will be evaluated, in immunologically-experienced humans.

Because Tri-NIV is produced at high yields in insect cells, it potentially presents a more costeffective method of producing large quantities of an annual seasonal influenza vaccine when compared to the traditional egg-based manufacturing processes, and if successful, may also offer a flexible and rapidly-responsive platform for production of novel influenza hemagglutinins from strains with pandemic potential. Initial development, however, will focus on potential superior benefits of a seasonal trivalent or quadrivalent formulation in the vulnerable older adult population.

Two Tri-NIV treatment groups evaluating either 15 or 60 μ g of HA antigen per strain have been proposed to 1) allow comparison with immunogenicity and safety profile of Fluzone HD and 2) evaluate the antigen dose response to inform further clinical development of the vaccine. The Matrix-M1 adjuvant, shown to remarkably enhance immunological responses of several vaccine antigens, with an overall acceptable safety profile in over 1,400 humans exposed to date, is proposed as the adjuvant of choice.

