2.2 Study Endpoints

2.2.1 Primary Endpoints

• Number and percentage (95% confidence interval [CI]) of subjects with solicited local and systemic adverse events over the 7 days post-injection (ie, Day 0 through Day 6 post-dosing); all adverse events (including adverse changes in clinical laboratory parameters) through 21 days post-injection; and MAEs, SAEs, and SNMCs through 1 year post-Day 0 dosing.

- Antibody titers specific for the HA receptor binding domains of each of the virus strains included in Tri-NIV as measured by the HAI assay. Derived/calculated endpoints based on these data will include:
 - Geometric mean titer (GMT) defined as the antilog of the mean of the log-transformed HAI titers for a given treatment group.
 - \circ Geometric mean ratio (GMR) defined as the ratio of post-vaccination and pre-vaccination HAI GMTs within the same treatment group (designated as GMR_{Post/Pre}).
 - Seroconversion rate (SCR) defined as the percentage of subjects with either a baseline HAI titer < 1:10 and a post-vaccination titer ≥ 1:40, or a baseline HAI titer ≥ 1:10 and a 4-fold increase in post-vaccination HAI titer relative to baseline.
 - Seroconversion rate difference defined as the difference of seroconversion rates between each of the Tri-NIV vaccine groups and Fluzone HD group and its upper 95% CI.
 - Seroprotection rate (SPR) defined as the percentage of subjects with an HAI titer \ge 1:40.

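### A stated reason for the Tri-NIV arms is safety comparison with Fluzone HD, but all planned safety estimates are within-group; a few descriptive risk differences would be a cheap improvement

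*SAP*

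**What the plan says.** The rationale (Protocol Synopsis and 1.8; SAP 1) gives two reasons for studying two Tri-NIV doses. The first is to "allow comparison with immunogenicity and safety profile of Fluzone HD"; the second is dose response.

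The safety plan is within-group throughout. The primary safety endpoint in SAP 2.2.1 is "Number and percentage (95% confidence interval [CI]) of subjects with solicited local and systemic adverse events over the 7 days post-injection", with matching summaries for other events. Protocol 10.4.1.1 states: "Safety analysis will be descriptive and based on the safety population". SAP 8.1 adds: "The number and percentage (95% CI) of subjects in each treatment group with a given term will be summarized". Neither document plans a risk difference or ratio for any safety endpoint. Protocol 3.1.1.1 mentions an imbalance against Fluzone HD, but only for medical review after a holding rule is met, and with no estimate attached.

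Immunogenicity is handled differently. SAP 7.1 says "Seroconversion rate difference is defined as the difference of seroconversion rates between each of the Tri-NIV vaccine groups and Fluzone HD group" and "The Newcombe method will be used to construct its 95% confidence interval". It treats seroprotection the same way and adds a between-group geometric mean ratio. Protocol 10.4.1.2 also plans intervals for the differences in both rates.

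Both sample-size sections carry one disclaimer for the whole trial: "No hypothesis tests are specified and the sample size is not intended to support any statistical contrast of Tri-NIV with Fluzone HD".

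**The concern.** Safety and immunogenicity are both primary objectives, both are framed as description, and both fall under the same sample-size disclaimer. Only immunogenicity gets an estimate of how each Tri-NIV group differs from Fluzone HD. No reason is given for treating them differently.

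The safety comparison is of real interest. This is the first human exposure to Tri-NIV with Matrix-M1. Protocol 1.9 reports short-term reactions in 40 to 60% of one-dose recipients of a different antigen with this adjuvant, against 27% with unadjuvanted antigen and 36% with placebo. A reader who wants to know whether Tri-NIV is more reactogenic than Fluzone HD will find two percentages and two separate intervals. If that reader judges by whether the intervals overlap, a moderate excess may pass as similarity. If someone computes differences later, the choice of endpoints will have been made after unblinding.

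**Working it through.** **The plan's own safety figures.** SAP 9 gives precision for single groups or pooled Tri-NIV only.
- Chance of at least one event: 1 − (1 − 0.021)^110 = 90.3% and 1 − (1 − 0.011)^220 = 91.2%, both above 90% as stated.
- One-sided 95% upper bound with no events: 1 − 0.05^(1/110) = 2.69% and 1 − 0.05^(1/220) = 1.35%, matching 2.7% and 1.4%.

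These reproduce. None concerns a difference from Fluzone HD.

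**Inputs for the illustration.**
- n = 110 per group (Protocol 3.1, SAP 1.1).
- Fluzone HD pain rate from Protocol 1.10: "including a 35.6% incidence of local injection site pain". The nearest count is 39/110 = 35.5%.
- Tri-NIV true rates of 50.0%, 50.6% and 55.6%: assumed, i.e. excesses of 14.4, 15 and 20 points.
- Per-group intervals: Clopper-Pearson, assumed. The SAP names no method for safety percentages; it names this one for seroconversion.
- Difference interval: Newcombe, as in SAP 7.1.

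**Formulas.** Wilson limits (l, u) for each group are [p + z²/2n ± z√(p(1−p)/n + z²/4n²)] / (1 + z²/n), with z = 1.96. For d = p₁ − p₂ (Tri-NIV minus Fluzone HD), the Newcombe limits are
- lower: d − √[(p₁ − l₁)² + (u₂ − p₂)²]
- upper: d + √[(u₁ − p₁)² + (p₂ − l₂)²]

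**Example 1: 55/110 against 39/110.**
- Clopper-Pearson: 40.3–59.7% and 26.6–45.1%. They overlap.
- Wilson: 40.82–59.18% and 27.14–44.75%; d = 14.55 points.
- Lower: 14.55 − √(9.18² + 9.29²) = 14.55 − 13.06 = 1.5.
- Upper: 14.55 + √(9.18² + 8.31²) = 14.55 + 12.38 = 26.9.
- The difference interval excludes zero.

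**Example 2: 60/110 against 39/110.** Clopper-Pearson gives 44.8–64.1% and 26.6–45.1%, which still overlap. The difference is 19.1 points (5.9 to 31.3). With Fluzone HD at 39/110, every Tri-NIV count from 54 to 60 gives overlapping per-group intervals and a difference interval above zero.

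**How often.** Sum binomial(x; 110, p_T) × binomial(y; 110, p_C) over all pairs (x, y) that meet each condition, with p_C = 35.6%:

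| Assumed true Tri-NIV rate | Newcombe interval above zero | Per-group intervals separate |
|---|---|---|
| 50.0% | 58% | 22% |
| 50.6% | 61% | 25% |
| 55.6% | 85% | 53% |

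In the first row, 57.6% − 22.3% = 35% of all trials would have a difference interval above zero with overlapping per-group intervals.

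**Chance findings from adding intervals.** With no true difference, one Newcombe interval excludes zero in about 5% of trials at a 35.6% rate, 4% at 10% and 2% at 2%. SAP Table 3 lists 23 solicited terms: 23 × 2 contrasts = 46 intervals, so roughly 46 × 0.02 to 46 × 0.05, or about 1 to 2 chance exclusions. Five composites give 5 × 2 = 10 intervals, so 10 × 0.02 to 10 × 0.05 = 0.2 to 0.5.

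**The case against.** The plan delivers what it promises. The objective is to describe, the endpoint is a per-group percentage with an interval, and SAP 8.1 supplies it. The comparison phrase is background rationale, not an objective or endpoint, and randomised concurrent groups shown side by side already permit comparison. All of this stands, so the plan does not contradict itself and no commitment is broken.

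A reader might infer that anyone using the tables has to compare intervals by overlap, and that a real excess will be hidden. The documents do not support that. No rule judges similarity by overlap, and the counts and percentages are reported: 50% beside 35% is plain to see, and the difference can be computed from the table. The figures above measure how weak overlap is as a yardstick, not a loss of information. Nor does any in-trial decision turn on it, because the Day 21 review has no cut points or stopping rules.

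A reader might also infer that the sample-size disclaimer concerns hypothesis tests only. It does not: its second clause covers any statistical contrast with Fluzone HD. What remains is that the same disclaimer did not prevent interval estimates for the immunogenicity differences. A labelled estimate claims no power, so the disclaimer does not rule out a few for safety.

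Finally, contrasts for every solicited term would invite chance findings. That objection is sound, and it limits the remedy to composites.

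**Conclusion.** A worthwhile, low-cost improvement to estimation and reporting, not an error. The trial says its arms allow a safety comparison with Fluzone HD, but it plans no estimate of one, while providing such estimates for immunogenicity under the same descriptive framing.

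The gain is a more sensitive and pre-specified basis for comparison. In the pain illustration, the difference interval shows an excess in 58 to 85% of trials, against 22 to 53% for separation of the per-group intervals. Those figures rest on the protocol's historical Fluzone HD rate, assumed Tri-NIV rates, full groups of 110 and assumed Clopper-Pearson intervals. Other rates or another interval method would move them. They do not show that the planned tables conceal anything or that the trial is undersized.

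Pre-specification has some weight because SAP 10 treats the Day 21 analyses as final and allows a report of them to go to regulators.

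**What to change.** In SAP 8.1.1 and 8.1.2, add for each Tri-NIV group minus Fluzone HD the risk difference with a Newcombe 95% confidence interval and no p-value, for this list only:

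- any solicited local event, Days 0–6
- any solicited systemic event, Days 0–6
- any grade 3 solicited event, Days 0–6
- any unsolicited adverse event in the 21-day dataset
- any related unsolicited adverse event in the 21-day dataset

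State that the intervals are descriptive, unadjusted for multiplicity and not powered. Keep individual solicited terms as per-group summaries. The list stays within Days 0–6 and the SAP 8.1.2 21-day dataset because later contrasts would also reflect licensed vaccine against placebo at Day 21.

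Cost: two extra columns in existing tables, ten unadjusted intervals with a modest risk of a chance exclusion of zero, and a footnote. The sample SAS code in SAP 7.1 already requests the Newcombe interval. Sample size and data collection do not change.
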